Satisfaction. Throughout the delivery of the intervention, the study team will determine the satisfaction with the intervention among participants in the intervention group (i.e., Group A- Grow Well) using brief surveys to assess mothers' and caregivers' perceptions of and satisfaction with the adapted curriculum. For the Grow Well group, after each in-person session and phone call check-in, the CHWs will provide participants with a QR code to access a brief satisfaction survey that will take about 5 minutes to complete. *Appendix W*. Brief Satisfaction Surveys includes both the survey to assess satisfaction after the in-home session and the survey to assess satisfaction after the phone call check ins. Additionally, at the completion of the intervention, study team members will conduct interviews with 15-20 participants (mothers and caregivers) in the intervention group (i.e., Group A- Grow Well). The interviews will assess perceptions of and satisfaction with the curriculum received. The interview will include open-ended questions about content, format, length, and cultural relevance of the curriculum (see *Appendix R*. Participant Satisfaction Interview). Study team members will conduct the interview by phone or Zoom after completion of the six-month study period. These interviews will be 30-45 minutes, audio recorded, and analyzed using rapid analytic techniques of template and matrix analysis as well as inductive approaches using MAXQDA qualitative analysis software. Participants will receive a gift card of \$25 for their time.

References

b) If you are using a dataset, please list out the variables you will be accessing. If you are using the Psychology Subject Pool, please list out the pre-screening data you will be collecting on your participants.

(Max ½ page)

NA

21. Deception

a) Does this study involve deception or intentional lack of disclosure?

Yes No

b) If YES, justify and indicate how participants will be debriefed. Indicate if participants are free to withdraw or selectively edit data after being fully debriefed. If NO, skip to the next question.

(Max ¼ page)

22. Research Results: If relevant, please describe what information/feedback, if any, will be provided to the subjects and/or communities after their participation in the project is complete. How will they be able to access the information? If relevant, describe the debriefing process.

(Max ¼ page)

Participants will be provided with our project webpage and social media handles (Facebook and Instagram @GrowWell_CrecerBien) where they can access additional information and resources (see *Appendix S*. Dissemination

Activity Website). We will inform participants that once the study is complete and community reports developed, study results will be shared with the community via the web page and social media platforms. The results will only be shared in aggregate meaning that individual data will not be shared/disseminated.

23. Consent Process - Ensure you are following the [UCR Informed Consent Guide](#). Sample Informed Consent Templates can be found on the [ORI Resources page](#).

a) Describe the process that will be used to obtain informed consent. How will it be recorded? Who will be authorized to conduct the process? Note that it's the quality of the consent that's most important not the format.

(Max ¼ page)

The study program coordinator will review the consent form via phone and obtain verbal consent from all participants prior to the start of data collection for all activities. For all participants partaking in in-person activities, which includes mothers or caregivers opting to complete the survey in person, infant anthropometric measurements either at the CVFC or at mother's home, and/or participation in in-person sessions, we will obtain written informed consent. This will occur at the first baseline data collection (survey or infant anthropometric measurements) or in-person intervention session (for participants randomized to Group A), whichever occurs first. Thus, all mothers (given that infant anthropometric data will be collected in person) will provide written informed consent. However, it is possible that for caregivers randomized to Group B and that choose virtual or phone data collection, we will not obtain written informed consent if in-person activities will take place. Participants will be provided a copy of the consent form via email, text, or hardcopy. The study team member will review the consent form, provide the opportunity for the participant to ask questions, and be made aware that they can stop their participation in the study at any point. Participants will be provided with a copy of the consent form and asked to follow along with the team member who will read out loud each section of the consent form. Participants will be given the opportunity to ask questions prior to providing their verbal consent. This procedure will be used with each participant.

During the consent process participants will be made aware that de-identified data sources including the transcripts of interviews, survey data, and infant anthropometric data will be de-identified. All records that include participants identifiers, such as the tracking files and audio files will be deleted after data collection and analysis. Participants will be informed that they can opt out of the study at any point during the 24-week study period and request for their data to not be included in the research. All participants will receive a study identification number to maintain confidentiality and privacy for all data collected. All data will be kept in a password-protected folder on the SOM secure server; once the data have been analyzed any records will be deleted (see Appendix T. Randomized Controlled Trial Consent – Mothers and Appendix U. Randomized Controlled Trial – Caregivers).

For mothers and caregivers in the intervention group (Group A- Grow Well), they will be given the option to opt into the satisfaction one-on-one interview and will be asked to provide their verbal consent (see Appendix Z. Consent – Participant Satisfaction Interview).

For the CHWs and healthcare staff in the one-on-one feasibility interviews they will be asked to provide their verbal consent (see Appendix V. Feasibility Consent - Community Health Workers and Healthcare Staff).

b) If you are applying for a waiver of documented consent (e.g., verbal, online, etc.) or a waiver or alteration of the consent process (e.g., not obtaining consent at all), please explain how you are meeting the conditions for the waiver or alteration as outlined in the [UCR informed Consent Guide](#).

(Max ¼ page)

In addition to written informed consent, we are also requesting a waiver of documented consent for data that will be collected via Zoom or phone. The electronic consent form will be on the Qualtrics platform and will be administered orally to all participants who will also be provided an electronic version of the consent form via the chat in Zoom or if calling into the Zoom platform, we will text or email them the consent form.

24. Will anyone other than the participants provide consent (e.g., parents, guardians, legally authorized representatives, etc.)? Describe the process by which capacity/competency will be assessed.

(Max ¼ page)

Because we will include infants who are approximately 4 months old, the mother enrolled in the study will provide consent for their infants to participate in the study. Specifically, infants will be involved in the collection of anthropometric measurements. If mothers chose not to provide consent for their infants to participate in anthropometric measurements, they will still be able to participate in the study

25. Withdrawal: Where applicable, please describe how participants will be informed of their right to withdraw from the study and outline the procedures that will be followed to allow them to exercise this right. Also, what will happen if data has already collected (e.g. previous data will be kept, all data will be destroyed, etc.)?

(Max ¼ page)

The consent form contains language indicating participants' right to withdraw from the study at any point. During the consent process, participants will be informed that they can opt out of the study at any point during the 24-week intervention study period or during the qualitative interviews (if they opt into this data collection activity) and request for their data to not be included in the research. At the beginning of the study, participants will receive a study identification number that will be linked to the data they provide. We will create a document that includes the participant's name and study ID #. Only select members of the investigative team, including [name] (PI), the project coordinator ([name]), and graduate student researcher ([name]) will have access to this file, which we will store on a password protected file on the UCR SOM server. Once all data collection is complete, we will destroy this file.

Thus, during the consent process, participants will be informed of their right to withdraw from the study at any time both in writing via the consent document and verbally from the consenting study investigator/team member. When reviewing the consent forms, the interviewer will inform participants about the voluntary nature of their participation and their right to withdraw from the study at any point during the research. The study team member will make clear the following: 1) the participant can notify the study investigators/staff of their wish to withdraw and 2) after confirmation of withdrawal; all data collected from the participant will be destroyed and will not be included in study analyses or deliverables. Participants will be able to leave any data collection activity at any time and can withdraw from the study at any point. Withdrawal will not affect their relationship to UCR or partnering healthcare systems such as UCR Health or the CVFC.

All data will be kept in a password-protected folder on the SOM secure server; once the data have been analyzed any records will be deleted.

26. Privacy, Confidentiality & Data

- a) **Privacy: Where and how will participants be providing information? Are the researchers collecting identifying information (e.g., names, addresses, phone numbers, DOBs, phone numbers, licenses, audio/video recordings, etc.)? If yes, please describe:**

(Max ¼ page)

Researchers will obtain participants' contact information, including cell phone and email address, to share information on accessing the Zoom platform and to call participants to schedule and conduct interviews. Postal addresses will also be obtained to mail out participant incentives (e.g., gift cards, welcome gift). Phone numbers, email addresses, and postal addresses will only be used for the purposes of data collection and compensation. The consent forms include an option to opt into future research on the health and wellbeing of Latino and Indigenous Latin American communities. For all those who opt into future research, their names and contact information will be recorded in a separate database only accessible to study team members.

To protect participant information when we collect survey data, we will remove all responses regarding incentive payment (e.g., address to send gift card) and place it on a separate document then delete the information once payment has been sent.

Furthermore, we will transcribe the audio file of the recorded one-on-one using a transcription service, Go Transcript, that will transcribe the audio recordings. After audio files are transcribed, a team member will then listen to the audio recording and review the transcribed document correcting for accuracy. In the correction process, transcripts will be de-identified meaning that names, places, or similar forms of identification will be removed.

Here is Go Transcript's policy for confidentiality/privacy and their protocol for storing data:

Go Transcript (gotranscript.com) has a Non-Disclosure Agreement:

- All transcribers must sign an NDA to assure clients of their secure transcription practices
- Transcriptionists sign job-specific NDAs for certain tasks as required by clients

Privacy and Confidentiality:

- All files are kept on Go Transcript servers only and are encrypted while sending them over the internet
- All files are cut into small parts of 5-10 mins. The whole file cannot be obtained by the same transcriptionist, no one will work on more than 1 part of the same file
- Actions of transcriptionists are always monitored
- After the transcription is complete, the file will be deleted off their system

b) Confidentiality: Describe the procedures used to protect the confidentiality of participants. If not relevant, describe any limitations to protecting the confidentiality of participants whether due to the law or method used (e.g., confidentiality is not appropriate). For storage of electronic identifiable information outside of a secure server environment, UCR requires the use of encryption software.

(Max ¼ page)

We will collect identifying information, including name, contact information, and address to distribute gift cards to participants. Name and contact information will be linked to a study identifying number (SIN) and stored on a password protected file. The SIN will be linked to pretest and posttest data, anthropometric body measurements, and qualitative interviews. The SIN will not be linked to any identifiers to protect participant confidentiality.

c) Data: Where will the data be stored and for how long? Who will have access to identifying information and for what reason?

(Max ¼ page)

Any data with identifiers such as tracking files will be stored until all data have been collected and analyzed. Digital copies of files such as survey responses and audio files will be stored in a password protected folder on the UCR School of Medicine secure server. Any data shared with study personnel including responses to socio-demographic

surveys, audio recordings of interviews, transcripts, will be stored on a password protected server accessible only by study personnel listed on the roster. At the end of the study, audio recordings will be deleted, and de-identified transcripts will be kept. Similarly, responses to the socio-demographic survey will be downloaded from Qualtrics as an excel file and the survey will be deleted from the Qualtrics platform. De-identified transcripts will be imported into MAXQDA, a qualitative data analysis software, for analysis purposes. Per NIH Per NIH's Data Management & Sharing Policy, participants will be informed via the consent forms that their data may be used for future research without their additional consent after identifiers have been removed from the data.

27. Possible Risks

a) Please check off all potential risks to participants as individuals or as members of a community or to the researchers that may arise from this research. Please acknowledge risks even if remote or unlikely.

Physical Risks (e.g., bodily contact, administration of substance):	 Yes  No
Psychological/emotional risks (e.g., feeling uncomfortable or upset):	 Yes  No
Social risks (e.g., economic, loss of status or reputation):	 Yes  No
Legal risks (e.g., arrest or subpoena):	 Yes  No

b) Describe the possible risks and consider the probability and magnitude of possible harms and discomforts. Describe the procedures that will be used to minimize potential risks to participants.

(Max ¼ page)

The focus of the research is on childhood obesity risk reduction and includes providing participants with education about healthy infant feeding practices and communication amongst caregivers. It may be emotionally and psychologically difficult to discuss children's health especially if mothers and caregivers have children or family with childhood obesity, diabetes, and related chronic health conditions. The study team will minimize these risks by creating a safe space for sharing during the delivery of infant nutrition education to mothers and caregivers. We will do this by informing participants that they do not have to answer any questions that might be uncomfortable. We will also let them know that we can take a break if they need to calm themselves, or that we can switch to a different, less difficult/uncomfortable topic.

This study includes infant anthropometric measurements. Obtaining infant height, weight, and percent fat using a caliber, can be uncomfortable for infants and they may cry. We will reduce this risk by training our team to collect these data as well as be mindful of infants' distress and stop data collection if infants are unable to stop crying. Additionally, a possible risk is breach of confidentiality as complete confidentiality cannot be guaranteed and its possible that participants may experience social risks, specifically loss of a day's wages. Many of the participants in our study are from farm working communities and often work on the weekends. We have purposefully decided to conduct research on Saturdays as people are less likely to work during the weekend than the weekdays. However, it is possible that participants may need to work during the time of the clinic. If this is the case, we will offer the option of a team member coming to the participant's home when it's convenient to them. If they then chose to bring their infant to the clinic it will be their decision.

A psychological/emotional risk of the study for mothers is regarding their postpartum mental health. There is a question on the pretest survey about self-harm. The specific question is: "The thought of harming myself has occurred to me." If the mother indicates "yes, quite often" or "sometimes" the interviewer will refer to the script on Appendix Y. The interviewer will follow the script to either connect the mother to the national suicide and crisis

lifeline- 988, and provide the resources with the mother and indicate mental health care services in the Inland Southern California region and check back in or pause to provide the mother with the mental health resources and then continue the interview.

28. Possible Benefits

a) Describe possible direct benefits to participants. If there are no direct benefits, please state so. Please note that compensation is not a benefit.

(Max ¼ page)

Participants may gain knowledge about healthy infant, child, and family eating, physical activity, and lifestyle changes. There may be potential benefit to others as there will be knowledge gained from participation in this program that participants can share with others in their family and community. Also, the information collected will help inform changes to improve early childhood obesity prevention programming.

b) Describe possible benefits to communities, society, or scientific knowledge in general.

(Max ¼ page)

This research has potential benefits for Latinx and Indigenous Latin American individuals, families, and communities as it can increase knowledge of chronic health conditions, especially early childhood obesity, and offer strategies to mitigate risk ultimately reducing disease burden.

29. The US research regulations define '*Minimal Risk*' as the probability and magnitude of physical or psychological harm that is normally encountered in the daily lives, or in the routine medical, dental, or psychological examination of healthy persons. (45 CFR 46 & 21 CFR 50)

a) Do you believe your proposed research activities meet the above definition of '*Minimal Risk*'?

Yes No

b) If yes, please elaborate by engaging your particular IRB proposal with the definition above.

(Max ¼ page)

This research does not require participants to share information that would create more distress than what is encountered in daily life or routine use of healthcare services.

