(Max ¼ page) This research uses community based participatory research (CBPR) to engage low-income Latinx families in research to pilot test an adapted nutrition education program compared to an existing nutrition education program. The goal of the research is to provide nutrition education on healthy infant feeding to reduce risk for early childhood obesity.
--

11. What is the scholarly rationale for this study?

(Max ½ page)

The prevalence of obesity in early life remains unacceptably high, especially among low-income children, most are ethnic minorities. Marked ethnic disparities are evident by two years of age, which suggests that existing interventions are not adequate. Early prevention is critical, especially for low-income children. For example, among Latino children high body mass index during infancy renders them three times more likely than other children to be obese by age 6. The disparity observed at this young age presents a window of opportunity to intervene early through existing nutrition programs that foster healthful eating habits, which track into childhood and continue into adulthood. Yet, few prevention programs intervene during infancy, and those that do, do not incorporate feeding styles and practices into nutrition education, do not account for the involvement of caregivers other than parents in infant feeding, and/or 3) start too late. The proposed research addresses these gaps by moving beyond healthy eating to better understand and promote healthy feeding. This project, which focuses on an-at-risk child population, has great potential to address our nation's growing crisis of childhood obesity, which can dramatically improve the health of millions of low-income children, their families, and their future children.

12. What are the study hypotheses or research questions?

(Max ¼ page)

This research will implement and evaluate an existing healthy infant feeding intervention, Healthy Beginnings, which was developed for English-speaking low-income mothers in Australia and delivered by public health nurses via in-home visits. We will test the efficacy of an adapted version of this intervention in comparison to the original intervention.

Aim 1. Pilot test an adapted nutrition education program of, compared to the original program curriculum.

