- Using a pilot randomized control trial with 30 mother-infant-caregiver triad (15 intervention, 15 control) determine the feasibility, acceptability, and preliminary efficacy of the adapted intervention compared to the original intervention. We hypothesize that the adapted intervention will be feasible, acceptable to study participants, and efficacious in addressing feeding styles and practices and caregivers' role in infant feeding.

We anticipate that the intervention will be feasible to deliver and acceptable to mothers and caregivers, and that the mother—infant-caregiver triads randomized to intervention with the adapted Healthy Beginnings curriculum compared to the treatment as usual control group will demonstrate greater improvements in outcomes (i.e., infant feeding knowledge and use of recommended feeding practices) after 6 months compared to the control group.

III – Study Design and Methodology

13. Study Timelines

Estimated start date for involvement of participants: February 1, 2023 or upon approval of the IRB protocol.

Estimated completion date for the involvement of participants: Feb. 28, 2024

14. Location of Research

a) Where will this study take place? If there is an online component, provide details.

(Max ¼ page)

The research will be carried out in Inland Southern California, specifically communities of the Coachella Valley and surrounding area. The PI, [name] and Co-Investigator [name], along with graduate and undergraduate research assistants are located at UCR. Co-I, [name], and research coordinator/assistant, [name], is located at Brown University. Community Investigator, [name], is located in the Coachella Valley. All research takes place at UCR. The research will primarily engage Latinx and Indigenous Mexican (e.g., Purépecha) communities in Inland southern California.

b) Is this a collaborative or multi-site study? Yes No

- Collaborative or cooperative studies involve investigators from two or more institutions working together to conduct a research project. Different research activities can occur at different sites or the study can be a single-site study that involves personnel from multiple institutions.
- Multi-site studies use the same research procedures outlined in a single protocol that is carried out at multiple institutions (e.g., a clinical trial where participants will be enrolled at each participating site, or an educational intervention implemented at each participating site).

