The pilot RCT will include an intervention and control group and will be carried out over 6 months or 24 weeks and will involve 30 mother-infant-caregiver triads. Both mother and caregiver have to agree to participate in the study to be enrolled. If the caregiver declines, then the mother cannot participate; and vice versa if the mother declines, then the caregiver cannot participate. The eligibility screening tool asks mothers if another caregiver who cares for their infant at least 3 hours per week would be willing to participate in the study with them. If the mother answers no, then the mother is not eligible to participate in the study. Enrollment is ongoing and will begin the first week of every month from April to August 2023. The mother-infant-caregiver triad will be enrolled in the study upon recruitment and begin the study as soon as the infant is 4 months of age, which aligns with the dissemination of packet 1 that includes nutrition education for families of infants 4 to 6 months of age. In this design, participants will be randomized into the intervention or control group: intervention group will be Group A: Grow Well and will

receive the adapted Healthy Beginnings Curriculum (n= 15 mother-infant-caregiver triad) and the control group will be Group B: Healthy Steps and will receive the Healthy Steps curriculum or treatment as usual as this is the curriculum commonly shared during well baby visits (n= 15 mother-infant-caregiver triad). Randomization will occur once base-line data is collected. Comparisons will be made between the intervention and control groups during the first 6 months of the intervention. The focus is on Latinx Spanish-speaking families; however, all our material is in English and Spanish to accommodate language preferences. Additionally, if a mother or caregiver prefers Purépecha, a language commonly spoken in the region, a Purépecha-speaking team member can translate orally from Spanish to Purépecha as this is an oral and not written language.

Intervention Design

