Group A - Grow Well. Our team collaborated with mothers and caregivers to adapt the Healthy Beginnings curriculum (<http://www.healthybeginnings.net.au>) for low-income Latinx immigrant families and communities. The curriculum focuses on healthy eating through education on nutritional content, parental and caregiver roles, and responsibilities for food preparation and family mealtimes. The intervention also encourages use of responsive feeding practices (i.e., responding to baby's hunger and fullness cues), as well as communication skills and conflict resolution strategies regarding baby's feeding. The original Healthy Beginnings curriculum includes material for mothers of infants 0 to 24 months. For the purposes of the pilot project, we will implement and evaluate material for infants 4 to 12 months (see *Appendix F. Adapted Healthy Beginning Modules 4 to 12 months*). The rationale for focusing on this age range is solid food introduction and transition to eating family meals occurs during this time. The intervention will be six months and include three components: 1) 30-45 minute monthly in-person delivery of material to mother and other caregivers; 2) 15-to-20-minute monthly phone call with mothers, and 3) being part of a WhatsApp group chat to receive weekly posts. Study team community health workers (CHWs) will deliver the intervention. All CHWs will participate in a training (in Spanish) on how to deliver the intervention prior to the start of the research.

In home sessions. For all in-home sessions, the CHWs will follow scripts. The scripts will provide instruction on delivering infant nutrition information, recommended infant feeding practices, and communication and conflict resolution strategies, and self-care practices for mothers and caregivers (see *Appendix G. Community Health Worker Scripts for In-home Sessions*). At the end of the in-home sessions, the CHW will work with the mothers and caregivers to set goals for infant care and feeding, communication strategies, and self care (see *Appendix H. Goal Setting*).

Phone calls. The CHWs will call (phone or video depending on participant preference) mothers one time per month of the intervention to check in on the goals and answer questions (see *Appendix G. Community Health Worker Scripts – refer to section for Phone Call Check ins with mother*). This call will occur two weeks after the in-home session and be approximately 15 to 20 minutes in length.

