WhatsApp group chat. Study team members will post weekly to a group chat that includes the mothers and caregivers in the intervention group (see *Appendix I. WhatsApp Posts*). The posts will include feeding information, infant nutrition, and caregiver communication. The posts are based on information provided in the adapted Healthy Beginnings 4–12-month booklets. The group chat will also be a virtual space for participants to interact and support each other. Mothers will be in one group chat and caregivers in a separate group chat. A team member will oversee this group and post weekly.

Group B - Healthy Steps. The control group will receive treatment as usual and will receive material frequently distributed throughout healthcare systems serving low-income patients. For the Healthy Steps curriculum for

infants 4 to 12 months of age packets are distributed at baby wellness visits at 4-, 6-, 9-, and 12-month visits (more information about the Healthy Steps program including handout material can be found here: <https://www.healthysteps.org/>). The Healthy Steps program provides information packets on developmental milestones, sleeping, and play (see *Appendix J. Healthy Steps Curriculum*). Healthcare providers hand out these packets to caregivers at the end of well-baby visits as take-home information. Mothers randomized to the control group will receive this information in the mail during first week of months 1, 3, and 5 of the study. The CHWs will call mothers the first week of months 1, 3, and 5 of the study to confirm receipt of the packets. Participants will be instructed to read the material. No other interaction will occur.

Zoom procedures

Zoom will be used for the orientation as well as baseline and follow up data collection and one-on-one interviews. We will create a password protected Zoom session with a unique link, meeting ID number and password per session that study team members will share directly with participants via text message or email (participants will be blind copied). Once participants enter the Zoom space, we will ask them to change their screen name to a pseudonym or will help them change the name, so their real name is not visible. Participants will have the option to keep their camera off or turn it on.

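### The research question and Aim 1 compare the adapted programme with original Healthy Beginnings, but no arm receives it; the only control is Healthy Steps/treatment as usual

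*Protocol*

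**What the plan says.** Section 12 of the protocol describes Healthy Beginnings, an existing programme developed in Australia, and then sets the research question: "We will test the efficacy of an adapted version of this intervention in comparison to the original intervention". Aim 1 reads: "Pilot test an adapted nutrition education program of, compared to the original program curriculum". The bullet under Aim 1 ties this to the randomised pilot of 30 triads, which is to determine, besides feasibility and acceptability, the "preliminary efficacy of the adapted intervention compared to the original intervention".

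The next paragraph of section 12 gives the outcome hypothesis. There the adapted curriculum is expected to do better after 6 months "compared to the treatment as usual control group".

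Section 20a defines two arms. Group A (Grow Well) receives adapted Healthy Beginnings, n = 15 triads. For the other 15, "the control group will be Group B: Healthy Steps and will receive the Healthy Steps curriculum or treatment as usual". The Orientation Session text names the same two groups and no third. The Group A description uses the word *original* once more, and ties it to a named programme: "The original Healthy Beginnings curriculum includes material for mothers of infants 0 to 24 months".

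**The concern.** The research question and the only numbered aim state an efficacy contrast that the trial does not randomise. Adapted versus original asks whether the adaptation adds anything to Healthy Beginnings. Grow Well versus Healthy Steps asks whether a whole package delivered by community health workers does better than mailed usual-care material. These are different estimands, and a result on the second says nothing about the first.

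The risk lies in reporting. A favourable difference written up against Aim 1 as worded would be read as evidence that the adapted curriculum outperforms original Healthy Beginnings, and no data in the trial bear on that.

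**Working it through.** No sample-size or power figure is involved. The check traces the comparator through each statement of the objective and then through the arms.

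**Comparator named, by place in the protocol**

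| Place | Comparator |
|---|---|
| Section 10, abstract | an existing programme, not named |
| Section 12, research question | the original intervention (the preceding sentence identifies Healthy Beginnings) |
| Section 12, Aim 1 | the original programme curriculum |
| Section 12, Aim 1 bullet | the original intervention |
| Section 12, outcome hypothesis | treatment as usual |
| Section 20a, arm definitions and Group B description | Healthy Steps/treatment as usual |
| Section 20a, Orientation Session | Healthy Steps |

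**Could *original* mean Healthy Steps?** Section 12 does not mention Healthy Steps. Section 20a says that Grow Well was adapted from Healthy Beginnings and uses *original* for that curriculum. Nothing says that Grow Well was adapted from Healthy Steps. The abstract does not settle the matter, because section 12 itself calls Healthy Beginnings an existing intervention.

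**Triads on the named comparator.** Total 30; Grow Well 15; Healthy Steps/treatment as usual 15.

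30 − 15 − 15 = 0 triads on original Healthy Beginnings.

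**Could Group A minus Group B stand in for the missing contrast?** Only if the arms differed in nothing but the adaptation. Planned intervention contact over the 6 months shows that they do not. The inputs are monthly sessions of 30 to 45 minutes (sections 15 and 20a) and, in section 20a, a "15-to-20-minute monthly phone call with mothers".

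- Group A, mothers: lower bound 6 × 30 + 6 × 15 = 180 + 90 = 270 min; upper bound 6 × 45 + 6 × 20 = 270 + 120 = 390 min.
- Group A, other caregivers (sessions only, since the calls are with mothers): 6 × 30 = 180 min to 6 × 45 = 270 min.
- Group A, both: weekly WhatsApp posts in addition.
- Group B: three mailings, and "The CHWs will call mothers the first week of months 1, 3, and 5 of the study to confirm receipt of the packets". The protocol then rules out further interaction. The length of these calls is not given, so no total in minutes is calculated.

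The arms therefore differ in programme, mode of delivery and amount of contact. The part of any difference that is due to the adaptation cannot be separated out. The Healthy Steps packets are in an appendix that is not shown, so nothing here depends on how much they say about feeding.

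**The case against.** The strongest reply is that this is a drafting slip and not a faulty design. The outcome hypothesis is the only comparative statement that gives outcomes, direction and time point, and it names treatment as usual. The opening of section 20a restates the trial's purposes with an intervention arm and a control group and does not mention the original curriculum. The arm definitions are clear, and staff working from section 20a would randomise, deliver and compare correctly. A report that described its arms would show the true comparator. Aim 1 is visibly garbled, which also suggests a slip. Differences in contact and delivery are inherent in any comparison of a package with usual care.

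Much of this stands. Adapted programme versus usual care is a legitimate pilot contrast, the conduct of the trial is not affected, and the harm arises only if results are reported against the aim as worded. The contact figures do not measure the defect; they show only why the randomised contrast cannot substitute for the stated one.

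The reply does not remove the error. Clear procedures show what will be done, but they do not correct a research question and an aim that say something else, three times in succession. Pilot status does not help either, since the bullet claims preliminary efficacy and even a preliminary estimate needs a correctly named comparator. A separate SAP could not cure it, because it cannot supply data on a programme that nobody receives.

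**Conclusion.** The concern holds. In three consecutive statements section 12 names a comparator that 0 of 30 triads receive, and its own outcome hypothesis contradicts them. The adapted-versus-original contrast is not estimable from this trial. What can be estimated, at pilot precision, is Grow Well as a whole package against mailed Healthy Steps/treatment as usual.

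The conclusion rests on reading *original* as Healthy Beginnings, which the sentence before the research question and the Group A description both support. It depends on no assumption about variance, effect size or drop-out. It is confined to the efficacy wording: the treatment-as-usual hypothesis and the feasibility and acceptability aims can still be addressed. Because the error sits in the research question and the only aim, it must be corrected.

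**What to change.** Amend section 12 in three places: the research question, Aim 1 and the bullet under Aim 1. Remove the comparison with the original intervention or curriculum from each. Replace it with the contrast already named in the outcome hypothesis: Grow Well (adapted Healthy Beginnings delivered by community health workers through home sessions, calls and WhatsApp) versus mailed Healthy Steps/treatment as usual. Name that comparator in the abstract as well, so that it cannot be read either way.

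Add one sentence saying that the trial gives a preliminary estimate of the effect of the whole package and that no conclusion will be drawn about adapted versus original Healthy Beginnings. Once the three phrases are corrected this sentence is a safeguard more than a necessity, but it costs nothing and fixes how results may be described.

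The cost is a wording amendment. Arms, sample and procedures stay as they are. The efficacy claim becomes narrower: package versus usual care.
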